7.9.1.2 Efficacy analyses

Analysis of the main criterion

The test for the non-inferiority of Lomatuell Pro® vs UrgoTul® for the main criterion will be carried out through a confidence interval (CI) approach. Non-inferiority will be established if the lower unilateral limit of the 97.5% CI in the PP population for the between-treatment difference (Lomatuell Pro® - UrgoTul®) in the percentage of wound dressing associated with a pain < 30 mm on VAS at V2 does not exceed -10%.

Considering that the studied population is "patients with an acute wound" and that the primary endpoint will be assessed at V2 (Day 3±2); we can expect very few drop-outs. We also expect few patients with a major protocol deviation. Therefore, we can conclude that an assumption of 10% attrition rate is acceptable for this study.

In order to unambiguously conclude to non-inferiority in agreement with most of guidelines, the same analysis will be performed on the mITT population. In case of missing data to evaluate the primary criterion, the subjects will be considered as failures. The trial will be considered positive if both approaches support noninferiority.

Adjustment

The frequency of analgesic intake will also be analysed. In case of a significant difference between the 2 dressing groups, the analysis of the primary criterion (painless dressing removals) will be adjusted using a Mantel-Haenszel test.

Analysis of the secondary criteria

The following statistical tests will be used to analyse the secondary criteria according to the criteria type:

- Qualitative nominal criteria will be compared using a Chi² test.
- Qualitative ordinal criteria will be compared using a Mann-Whitney-Wilcoxon test
- Quantitative criteria will be compared using an analysis of variance (ANOVA)

Degree of significance

The criteria for which the degree of significance of the bilateral test will not exceed 0.05 (statistically significant difference) will highlight the specificities between the 2 groups of dressing.

Percentage of complete healing at V3

A wound will be considered as completely healed when there is 100% of epithelialization (first epithelia layer) of the wound. The percentage of wounds healed will be calculated based on a blind assessment from photographs using W.H.A.T.

Assessment of the wound condition

The wound bed condition will be evaluated at V1, V2 and V3 or ET regarding 6 condition items - bleeding, maceration, inflammation, infection, ratio necrotic/ fibrinous/ granulation/ epithelisation tissue, and tissue in-growth in the dressing holes by means of the following 4-points scale: *none*, *mild*, *moderate*, *severe*. The percentage of each modality for each condition items will be calculated.

Assessment of the surrounding skin condition

The condition of the surrounding skin will be assessed at V1, V2 and V3 or ET regarding different conditions: inflammatory signs, irritation, allergic rash/eczema, blistering, skin stripping, maceration, dry, trauma to wound edges, product degradation on the skin, hematoma, other. These condition items will be assessed by means of the scale *Yes/No*. The percentage of each modality will be calculated.

Wound closure according to inclusion wound exudation status.

This will use a Cochran-Mantel-Haenszel test including treatment groups and baseline wound exudation status (none, light and moderate/heavy).

Global assessment of the dressing by the investigator

The global assessment of the dressing will be performed by the investigator at V2 and V3 or ET. Each item will be evaluated by means of the following scale: *very good, good, poor, and very poor*.

The percentage of each modality of each criterion (ease of handling, ability to maintain its integrity, ease of application, ability to be repositioned during application, conformability, wound adhesion, ability of dressings to stay in place, transparency, ability to transfer wound fluid to the secondary dressing, ease / speed of removal, overall impression, and absence of residue) will be calculated.

Global assessment of the dressing by the subject

A global assessment of the dressing will be performed by the subject at V3 or ET. Each item (ability to maintain its integrity, ability of dressings to stay in place, transparency, comfort of the patient, ability to transfer wound fluid to the secondary dressing, ease/speed of removal, overall impression) will be evaluated by means of the following scale: *very good, good, moderate, poor, very poor.* The percentage of each modality will be presented.

Assessments from the study nurse's booklet at each dressing change

The total number of dressing changes will be calculated and the mean value of dressing changes will be calculated.

For the other parameters (appearance of the dressing before removal, bleeding of the wound, condition of the wound, cleaning is required on or around the wound and type of solution used), the statistical unit is not the patient but the dressing change. The percentage of each modality of the other parameters will be calculated.

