7.9.1.1 Population Analyses

Analyses will be performed on three populations as follows:

• The Safety population consists of all subjects allocated to treatment sample; and who had at least one investigational product applied.

- All randomized subjects with at least one exposure to either dressing will be included in the modified intent-to-treat (mITT) population. Subjects will be analysed in the treatment groups to which they will be randomly assigned (as per ITT principle).
- The per-protocol (PP) population consists of all enrolled subjects who satisfied the entry criteria of the investigation, who had an assessment of main criterion at V2 and who completed the treatment without major violations of the protocol.

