7.9.2 Determination of Sample Size

A number of n = 75 subjects per group will allow a 80% power to demonstrate non-inferiority with a type I error of 2.5% one-sided considering 95% of dressing changes with a pain VAS value < 30 mm at D3 and a 10% non-inferiority margin, as recommended by the sponsor. Thus, considering an attrition rate equal to 10%, it is necessary to include n = 84 subjects per group to obtain the required power.

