10.2 Protocol Deviations

General definition: major protocol deviations are any protocol deviations that might significantly affect the completeness, accuracy, or reliability of the study data or that might significantly affect a subject's rights, safety, or well-being. Relevant major protocol deviations may include errors in treatment assignment, the use of excluded medication, poor compliance, loss to follow-up and missing data (cf. ICH E3. Questions and answers (R1). January 2013 and ICH E9).

In this trial, the following protocol deviations will be considered as major and will therefore lead to exclude patients from the PP set:

- Patient randomized while an inclusion criterion is not met
- Patient randomized while an exclusion criterion is met
- Patient not treated as per protocol between V1 (D0) and V2 (D3±2):
 - Patient randomized to Lomatuell Pro® but actually received UrgoTul® at D0
 - o Patient randomized to UrgoTul® but actually received Lomatuell Pro® at D0
- Pain assessment (VAS) during removal at V2 (D3±2) is missing (i.e. primary endpoint is missing)
- Pain assessment (VAS) during removal at V2 performed out of the time-window (i.e. at D6 or later)

Further major protocol deviations may be defined during the conduct of the trial, if deemed relevant. The list of major protocol deviations will have to be finalized and documented (for example, in the data review minutes) prior to the database lock.

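### The non-inferiority rule is reversed as worded and names no interval, and no usual interval gives the stated 80% power with 2.5% error, for PP alone or for PP and mITT jointly

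*Protocol*

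**What the plan says.** Protocol 7.9.1.2 (Efficacy analyses) tests the main criterion through a confidence interval, with no method named. Non-inferiority is concluded in the PP population if the lower one-sided 97.5% limit for Lomatuell Pro minus UrgoTul in the "percentage of wound dressing associated with a pain < 30 mm on VAS at V2 does not exceed -10" per cent.

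The same section repeats the analysis in the mITT population. There, "In case of missing data to evaluate the primary criterion, the subjects will be considered as failures", and "The trial will be considered positive if both approaches support noninferiority". It also states that "an assumption of 10% attrition rate is acceptable for this study".

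Protocol 7.9.1.1 defines the second set: "All randomized subjects with at least one exposure to either dressing will be included in the modified intent-to-treat (mITT) population". Protocol 10.2 removes from PP any patient whose V2 removal pain score is absent ("i.e. primary endpoint is missing"), along with eligibility failures, wrong-dressing cases and out-of-window assessments.

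Protocol 7.9.2 says that 75 per group, with 95% success and a 10% margin, "will allow a 80% power to demonstrate non-inferiority with a type I error of 2.5% one-sided". With 10% attrition, "it is necessary to include n = 84 subjects per group to obtain the required power".

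The supplied SAP does not settle the method. Its section 4 bases it on the Suprasorb C protocol, and its section 7.2 plans no formal comparison.

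**The concern.** There are three linked defects in the one rule that decides the trial.

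1. **Direction.** The endpoint is a success percentage and the difference is new minus comparator, so non-inferiority needs a lower limit greater than -10%. As written, success requires a limit at or below -10%.
2. **Interval.** At 95% success, 75 patients give 75 × 0.05 = 3.75 expected failures per arm. With so few events the common intervals for a difference in proportions disagree materially. A method still open when the data are seen could be chosen on the result.
3. **Joint rule.** 7.9.2 sizes a single comparison, but success needs two. A patient with a missing V2 pain score leaves PP and counts as a failure in mITT, so the attrition allowance that protects PP lowers the success rate in mITT.

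At stake is whether the trial has the 80% power and 2.5% error that the protocol states.

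**Working it through.** **Inputs.** From 7.9.2: 95% success (taken as equal in both arms), margin 10 points, one-sided error 2.5%, power 80%, 75 evaluable and 84 enrolled per group. From 7.9.1.2: PP and mITT must both pass, and missing counts as failure in mITT. Allocation is 1:1 (7.9.3).

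**The plan's own figure.** n = (1.960 + 0.8416)² × 2 × 0.95 × 0.05 / 0.10² = 74.56, so 75. Then 75 / 0.9 = 83.3, so 84. Both reproduce; there is no arithmetic error.

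**Literal wording, PP, 75 per arm.** The probability that the limit is at or below -10% is 18% (Wald) to 28% (Newcombe) when both arms are at 95%. It is 96% to 97% when Lomatuell Pro is truly at 85% against 95%. All results below use the intended direction, limit greater than -10%.

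**PP alone, 75 per arm.** All 76 × 76 outcomes were enumerated with binomial weights: power at 95% v 95%, error at 85% v 95%.

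| Interval | Power | Error |
|---|---|---|
| Wald | 81.7% | 3.69% |
| Newcombe | 71.8% | 2.57% |
| Miettinen-Nurminen | 68.6% | 2.02% |

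With both arms at 95%, Wald passes and Newcombe fails in 9.9% of trials; Wald passes and Miettinen-Nurminen fails in 13.1%. The reverse does not occur.

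Example, 70/75 v 72/75, difference 0.9333 - 0.9600 = -0.0267:
- Wald: -0.0267 - 1.960 × √(0.9333 × 0.0667/75 + 0.96 × 0.04/75) = -0.0267 - 1.960 × 0.0366 = -9.8%, a pass.
- Newcombe: the Wilson lower limit for 70/75 is 0.8532 and the Wilson upper limit for 72/75 is 0.9863. So -0.0267 - √((0.9333 - 0.8532)² + (0.9863 - 0.9600)²) = -11.1%, a fail.

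**Joint rule.** In each arm, PP successes are Bin(PP, p). Excluded patients with data contribute Bin(mITT - PP - m, p), and the m patients with a missing outcome are failures. Both tests must pass. The documents do not divide the 10% attrition among untreated patients (who leave both sets), missing outcomes and other PP exclusions, so m is an assumption and arms are taken as equal.

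Joint power with 75 PP of 84 mITT per arm:

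| Missing among the 9 excluded per arm | Wald | Newcombe | Miettinen-Nurminen |
|---|---|---|---|
| 0 | 79.1% | 69.5% | 65.7% |
| 4 | 65.0% | 59.6% | 56.2% |
| 9 | 41.3% | 37.6% | 37.6% |

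More favourable cases:
- 84 mITT, 0 to 4 excluded per arm, none missing: Wald power 83.7% down to 80.9%, error 3.3% down to 2.8%.
- 75 PP with 75 to 77 mITT, none missing, the rest untreated: Wald power 80.4% to 81.7%, error 3.1% to 3.7%.
- 84 mITT, one missing outcome per arm and no other exclusion: Wald 79.1%, Newcombe 73.6%, Miettinen-Nurminen 69.1% power.

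**Full grid.** mITT 75 to 84, PP from 75 to mITT, m from 0 to mITT - PP. The number of splits is the sum of (k+1)(k+2)/2 for k = mITT - 75 = 0 to 9, which is 220.

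| Interval | Splits with power ≥ 80% | Highest power | Splits with error > 2.5% | Highest error | Both targets met |
|---|---|---|---|---|---|
| Wald | 29, all with m = 0 | 84.6% | 84 | 3.69% | 0 |
| Newcombe | 0 | 77.5% | 3 | 2.57% | 0 |
| Miettinen-Nurminen | 0 | 74.3% | 0 | 2.37% | 0 |

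In the 29 Wald splits that reach 80% power, joint error is 2.82% to 3.69%.

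**The case against.** **Near miss.** At the plan's own numbers, 75 PP of 84 with no missing outcome, Wald gives 79.1% joint power and 2.45% error, within a point of the stated power and inside the stated error. That is correct, but it needs all nine excluded patients per arm to have a usable pain score. One missing value per arm lowers power to 77.3%. With none missing, the error is 2.9% to 3.8% at comparator rates of 97% to 99%.

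**The grid is a construct.** The 220 splits assume equal arms and fixed attrition, and counting them attaches no likelihood to any. 7.9.1.2 expects few drop-outs and few major deviations, so about 40% power is the extreme end. This stands: joint power is conditional on an unstated split. A Wald check with unequal arms (84 mITT per arm, up to 2 missing) also found no split meeting both targets; the closest was 80.05% power with 2.60% error.

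**Another SAP may name the interval.** Possible, since this trial's own SAP is not among the documents. The claim is only that the supplied documents do not name one.

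**The wording is a slip.** Agreed: the objective in 6.1 and the margin in 7.9.2 leave one workable reading. It is still the trial's only primary decision sentence.

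**Discordance is PP only.** The 9.9% and 13.1% describe the PP result, not the trial's overall conclusion. That limit is accepted.

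**Newcombe also exceeds 2.5%.** True, at 2.57%, by far less than Wald's 3.69%. Where strict control is wanted, Miettinen-Nurminen is the safer of the two at this design point.

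**Conclusion.** The concern holds. The inequality is reversed as written, and the supplied documents name no interval. For PP alone at 75 per arm, Wald meets the stated power but not the error, Newcombe misses power by about 8 points and error by 0.07 point, and Miettinen-Nurminen meets the error but misses power by about 11 points.

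For the joint rule, none of the three intervals gives both 80% power and 2.5% error in any of the 220 splits. How far joint power falls short depends on the missing-outcome count: from about 1 point (Wald, nine excluded, none missing) to about 40 points (all nine missing).

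These figures rest on 95% success in both arms for power, 85% v 95% for error, equal arms and the assumed attrition splits. The sample size arithmetic is sound for its formula; what is missing is a link from that formula to a named interval and to the joint rule.

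**What to change.** In 7.9.1.2, replace the decision sentence with: *Non-inferiority is established if the lower limit of the two-sided 95% Miettinen-Nurminen interval for Lomatuell Pro minus UrgoTul is greater than -10%, in both the PP and the mITT populations.* Newcombe may be named instead; one of the two must be fixed before database lock.

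In 7.9.2, restate power for the named interval:
- PP only at 75 evaluable per group: about 69% (Miettinen-Nurminen) or 72% (Newcombe).
- Joint PP and mITT, with the assumed attrition split written down. For 75 PP of 84 mITT: about 66% or 70% with no missing outcome, and 56% or 60% with 4 missing per arm.

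The cost is one sentence and a less favourable power statement. No patients, visits or data are added if that power is accepted. If 80% is to be kept for PP alone, about 93 (Newcombe) or 96 (Miettinen-Nurminen) evaluable patients per arm would be needed, before any allowance for attrition or for the joint rule.

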7.2.2.2 Intermediate visit (V2, D3±2)

The intermediate visit must be planned three days after the first investigational product application. If appropriate, a window of two days before or after this expected visit is allowed to make sure that the patient will have the first dressing change as early as necessary according to their condition (i.e. already on the next day after V1).

Adverse events (AEs) / Serious adverse events (SAEs) / Adverse device effects (ADEs) and Device deficiencies (DDs) occurring since the previous visit will be collected by the investigator. Any changes to the concomitant therapy will also be collected. The investigator will also ensure that the subject continue the investigation.

The presence of complete healing status (100% of epithelialization, first epithelia layer) of the wound) will be assessed.

NB! In case of complete epithelialization all procedures, required for Visit 3 should be

performed, data is to be recorded in the CRF section Visit 3. Visit 2 should be marked as "Not performed due to early epithelialization" in the CRF.

Depending on the subject condition, analgesics may be concomitantly prescribed by the investigator. In this case, details on the type of prescribed treatments belonging to analgesic therapeutic class as well as hour of intake before removal (within 2 hours notably) will be recorded in the CRF.

A photograph of the wound with the investigational product in place will be taken before product removal (but after secondary dressing removal, if there was any), according to the photography guidelines (see Appendix 17.1).

The investigator will remove the investigational product by following the standardized removal procedure (see Appendix 17.2). Data about dressing soak will be collected in the CRF.

Pain at the first dressing removal will be assessed by using the visual analogue scale (VAS). The investigator will ask the subject to assess his/her pain level at the dressing removal. The subject will be asked to rate the pain he/she felt at the moment of dressing change using the VAS tool.

After product removal, a photograph of the wound will be taken according to the photography guidelines.

The investigator will assess the wound and surrounding skin condition:

- Wound size estimation
- Assessment of the wound bed (bleeding, maceration, inflammation, infection, ratio necrotic/ fibrinous/ granulation/ epithelisation tissue, and tissue in-growth in the dressing holes)

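### The stated 80% power does not apply to the trial's own success rule: requiring both PP and mITT with missing counted as failure gives about 79% down to 44%, depending on how many V2 scores are missing

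*Protocol*

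**What the plan says.** Protocol 7.9.2 states that 75 subjects per group "will allow a 80% power to demonstrate non-inferiority" at a "type I error of 2.5% one-sided", with a 95% rate of removals scored below 30 mm and a 10% margin. It then allows for 10% attrition and says "it is necessary to include n = 84 subjects per group to obtain the required power". It names no analysis population.

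Protocol 7.9.1.2 tests non-inferiority first in PP and repeats the test in mITT. For mITT it says: "In case of missing data to evaluate the primary criterion, the subjects will be considered as failures". The decision rule is: "The trial will be considered positive if both approaches support noninferiority". The 10% attrition is defended on the ground that "we can expect very few drop-outs. We also expect few patients with a major protocol deviation", with no split between the two.

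Under 7.9.1.1, mITT holds every randomised subject with at least one exposure. Under 10.2, PP drops subjects with no V2 score, and also subjects who do have one but were ineligible, received the wrong dressing, or were assessed at D6 or later.

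The SAP supplied does not fill the gap. Its section 4 bases it on the protocol for another product (Suprasorb C), and its section 7.2 plans no formal comparison.

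**The concern.** A reader of 7.9.2 will take 80% as the chance that the trial succeeds if the dressings are equal. It is the chance of passing one of two tests, both of which are required.

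Dividing by 0.9 treats lost subjects as neutral: they shrink the sample and do nothing else. That is true in PP. In mITT the same subjects stay in the denominator, and those without a V2 score count as failures. This lowers the success rate in both arms, moves it away from 95% and widens the interval against a fixed 10-point margin.

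What is at stake is a false negative: two equivalent dressings, and a trial that fails because of a few unrecorded scores. The decision rule itself is conservative.

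**Working it through.** **Inputs.** From Protocol 7.9.2: one-sided 2.5%, power 80%, success rate 95% (taken as equal in both arms), margin 10 points, attrition 10%, 84 randomised per group. From 7.9.1.2: both analyses must pass, and missing = failure in mITT. Assumed, because the plan does not say: Wald limits, attrition equal between arms and unrelated to outcome, and every randomised subject exposed.

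**Step 1: reproduce the plan's figure.**

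n = (1.960 + 0.842)² × 2 × 0.95 × 0.05 / 0.10² = 7.851 × 0.095 / 0.01 = 74.6, so 75.

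75 / 0.9 = 83.3, so 84.

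Both numbers reproduce. They match PP, the analysis that loses all attrition cases: 84 × 0.9 = 75.6 evaluable per arm.

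**Step 2: mITT alone, closed form.** If a share m has no V2 score, the mITT success rate is p = 0.95 × (1 − m), and power is Φ(0.10 / √(2p(1 − p)/84) − 1.960).

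| m | p | √(2p(1 − p)/84) | mITT power |
|---|---|---|---|
| 0% | 0.950 | 0.0336 | 84% |
| 2% | 0.931 | 0.0391 | 72% |
| 5% | 0.9025 | 0.0458 | 59% |
| 10% | 0.855 | 0.0543 | 45% |

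**Step 3: both tests together, by simulation.** Each subject has no V2 score (probability m), or has a score but is excluded from PP for another reason (probability 0.10 − m), or is evaluable in both sets. True success is 95%. An analysis passes if the lower Wald limit (one-sided 97.5%) is above −10%. There were 1,000,000 trials per row.

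| No V2 score | PP | mITT | Both |
|---|---|---|---|
| 0% | 80.6% | 83.7% | 78.5% |
| 1% | 80.6% | 78.1% | 73.8% |
| 2% | 80.6% | 72.8% | 68.9% |
| 5% | 80.5% | 60.2% | 57.0% |
| 7% | 80.6% | 53.7% | 50.9% |
| 7.5% | 80.6% | 52.4% | 49.6% |
| 10% | 80.6% | 46.5% | 43.9% |

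Failure becomes more likely than success at about 7 to 7.5% missing.

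**Step 4: less attrition than planned.** Joint power is 84% with no attrition, 76% with 1% missing plus 2% other exclusions, 75% with 1% plus 4%, and 70% with 2% plus 3%. With no missing score and 2%, 4%, 5% or 6% other exclusions it is 83%, 82%, 81% and 80%.

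**Step 5: type I error.** With true rates of 85% against 95%, the two tests together pass in 2.4% of trials at 0% missing and in 1.4% at 10% missing. There is no inflation.

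**Step 6: size needed for about 80% on the joint rule at 10% attrition.** This takes 88, 108, 142 or 196 per group at 0%, 2%, 5% or 10% missing.

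**The case against.** The sample size contains no arithmetic error: 75 and 84 are right for the test they describe. That the 80% belongs to PP is an inference, because 7.9.2 names no population. Both points stand. The inference is firm, because the attrition allowance makes sense only for the analysis that discards those subjects.

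The stronger objection is that 44% is a corner case. It needs the whole 10% to be missing V2 scores, while the protocol expects very few drop-outs and 10.2 lists several exclusions that keep a score. Section 7.9.1.1 also asks PP subjects to have completed treatment, so someone who leaves after V2 drops out of PP but keeps the score in mITT. With no missing scores and up to about 6% other exclusions, joint power is 80% or more. If the whole 10% were randomised but never exposed, they would leave both sets and joint power would be just above 80%, though this is unlikely because the dressing is applied at V1. All of this stands and favours the upper part of the range.

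It does not make the missing share zero. A V2 score can be absent without drop-out: 7.2.2.2 has V2 recorded as "Not performed due to early epithelialization" when the wound has already closed, and Table 1 schedules the removal VAS at V2 only. The protocol gives no frequency for this and does not say whether such a subject counts as missing, so it supports no particular share.

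The exact values also depend on unstated choices. With Newcombe limits, joint power at 0% missing is 68.6%, a loss that has nothing to do with the missing-data rule. With a true rate of 97%, joint power is 92% at 0% missing and 82% at 2%. The direction is secure; the percentages hold under the stated assumptions.

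**Conclusion.** The concern holds. The 80% in 7.9.2 is not the power of the success rule in 7.9.1.2. At the planned 10% attrition, for any division between missing scores and scored deviations, joint power is below 80%: slightly below (78.5%) if no V2 score is missing, about 11 points below at 2% missing, and about 44% if every attrition case lacks a score. The protocol's own expectations point to the upper part of this range. If attrition proves small and no score is missing, joint power reaches 80 to 84%.

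These figures assume 95% success in both arms, missingness equal between arms and unrelated to outcome, all randomised subjects exposed, and Wald limits. The consequence is a higher chance of a false negative and a stated power that is too favourable. This should be corrected, but it does not threaten the validity of a positive result.

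**What to change.** In Protocol 7.9.2, state that the 80% refers to the PP analysis, add the power of the joint rule, and name the interval method in 7.9.1.2 and 7.9.2. Suggested text: *With 84 randomised per group, 95% success in both arms, 10% total attrition and Wald limits, the power to show non-inferiority in both PP and mITT is about 79%, 74%, 69%, 57% and 44% if 0%, 1%, 2%, 5% and 10% of subjects have no V2 score.* If another interval method is chosen, recompute these figures.

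Keep missing = failure as the prespecified mITT rule. Multiple imputation with a tipping-point analysis could be added, but only as a sensitivity analysis.

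The cost is a reworded paragraph and a less favourable stated power, with no added patients. The rewording does not raise the power. The larger samples in the last step of the working show what that would take, and they are not requested here.

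### Whether the primary pain result is checked against analgesic cover depends on a low-powered significance test; the check should be pre-specified and always reported

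*Protocol*

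**What the plan says.** Protocol 7.9.1.2 judges non-inferiority by the lower one-sided 97.5% limit for the difference (Lomatuell Pro minus UrgoTul) in the share of V2 removals below 30 mm, against -10%. The per-protocol (PP) and mITT populations must both succeed. Under Adjustment it adds that "The frequency of analgesic intake will also be analysed" and then: "In case of a significant difference between the 2 dressing groups, the analysis of the primary criterion (painless dressing removals) will be adjusted", by a Mantel-Haenszel test. It does not name the intake variable, visit, test or significance level for this step. The only between-group level in the section is the one for secondary criteria: "The criteria for which the degree of significance of the bilateral test will not exceed 0.05".

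The sample was sized for the primary comparison alone: "A number of n = 75 subjects per group will allow a 80% power to demonstrate non-inferiority" (Protocol 7.9.2). Analgesics may be prescribed at V2, where the endpoint is measured, and then the "hour of intake before removal (within 2 hours notably) will be recorded in the CRF" (Protocol 7.2.2.2).

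No adjusted or sensitivity analysis is planned independently of the test. The SAP supplied is written for another product (Suprasorb C), plans no formal comparison, and does not address this rule.

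**The concern.** Analgesia taken shortly before removal can bring a VAS score below 30 mm whatever the dressing does. In an open-label trial, prescribing may differ between arms. More cover in the Lomatuell Pro arm would move the observed difference towards non-inferiority. The protocol accepts this as a reason to alter the primary analysis, but makes the alteration depend on a test that was never sized to find such an imbalance. A non-significant result does not show that cover was similar. Yet under the rule it means the report contains no analysis that takes cover into account. Letting a preliminary p-value choose between two primary analyses also means that the 2.5% error level is not a property of the whole procedure.

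**Working it through.** **Inputs from Protocol 7.9.2.** "type I error of 2.5% one-sided considering 95% of dressing changes with a pain VAS value < 30 mm at D3"; "a 10% non-inferiority margin, as recommended by the sponsor"; 80% power; 75 evaluable per group; "considering an attrition rate equal to 10%, it is necessary to include n = 84 subjects per group".

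**Assumptions, because the documents give no figure.** Intake is a yes/no variable at V2. The gate is a Pearson chi-square test at two-sided 0.05, the level stated for secondary criteria. Use in the lower-use arm is 10-40%, widened to 5-80% as a sensitivity range.

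**Step 1: the plan's own figure.** n = (1.960 + 0.842)² × 2 × 0.95 × 0.05 / 0.10² = 74.56, so 75 per group; power at 75 is 80.2%. Attrition: 75 / 0.90 = 83.3, so 84. Both figures reproduce.

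**Step 2: how often the gate misses a true excess.** Miss rate = probability that the chi-square test is non-significant, by exact enumeration of two binomials.

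| True use, lower vs higher arm | 75 per arm | 84 per arm |
|---|---|---|
| 10% vs 20% | 59% | 56% |
| 20% vs 30% | 71% | 68% |
| 30% vs 40% | 75% | 73% |
| 40% vs 50% | 75% | 74% |
| 10% vs 25% | 30% | 26% |
| 20% vs 35% | 46% | 41% |
| 30% vs 45% | 51% | 48% |
| 40% vs 55% | 53% | 49% |

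The range is 26-75%. With lower-arm use anywhere from 5% to 80% it is about 13-76%. Seen from the other side, with lower-arm use of 20-40% the observed imbalance must reach about 14-16 points before adjustment is triggered (11-12 patients of 75, or 12-13 of 84). For example, 15/75 vs 25/75 gives chi-square 3.41 (not significant) and 15/75 vs 26/75 gives 4.06 (significant).

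**Step 3: what the whole gated procedure does to the claim.** Simulation with 75 per arm. The unadjusted limit is Wald. When the gate triggers, the Mantel-Haenszel risk difference with Sato variance is used. The true difference is exactly -10 points in each analgesic stratum.

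| Setting (painless rates UrgoTul / Lomatuell Pro) | Use, UrgoTul vs Lomatuell Pro | Gated procedure claims | Always-stratified claims |
|---|---|---|---|
| Uncovered 80/70%, covered 100/90% | 20% vs 35% | 3.6% | 2.7% |
| Same rates, excess reversed | 35% vs 20% | 2.1% | not needed here |
| Uncovered 94/84%, covered 99/89% (UrgoTul at 95% overall) | 20% vs 35% | 4.1% | 3.7% |

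In the first row the gate is non-significant in 46% of trials. Within those, the unadjusted claim is made about 4.6% of the time, so 0.46 × 4.6% = 2.1% of all trials carry an unadjusted claim after a missed gate. In the third setting, the Wald limit already claims 3.7% when use is equal, so the gate adds about 0.4 points.

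**Step 4: which difference is at -10.** These rates are errors only about the difference at equal cover. In the first row the overall rates are 0.8 × 80 + 0.2 × 100 = 84% for UrgoTul and 0.65 × 70 + 0.35 × 90 = 77% for Lomatuell Pro, an overall difference of -7. In the third they are 95% and 0.65 × 84 + 0.35 × 89 = 85.75%, a difference of -9.25.

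**The case against.** The strongest reply is that V2 intake comes after randomisation and may respond to the wound or to earlier painful care. The unadjusted randomised difference is then a legitimate primary estimate, and stratifying by intake can itself introduce bias. This stands. It rules out making the stratified result decisive, but it does not defend a rule that lets the same adjustment change the primary analysis when a p-value falls below a threshold.

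Second, the intake variable is undefined. Protocol 7.6 ties frequency of use to D0 and lists hour of intake before removal separately. If the gate uses D0 intake, randomisation leaves no true excess to miss and Step 2 does not apply. An ordinal frequency would also have different miss rates. This stands too, and is a further reason to name the variable.

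Third, a reader might infer that the error rate rises to 7.1%, the rate at which the unadjusted limit claims non-inferiority in the first setting of Step 3. That figure describes a rule with no gate, which is not the protocol's rule. A reader might also construct a case in which analgesia abolishes the dressing difference in covered patients and count the resulting claims as false. With uncovered 95% vs 85%, covered 100% in both arms and use 20% vs 35%, the overall difference is 90.25 - 96 = -5.75 and the stratified one averages about -7.4. Both lie inside the margin, so those claims are not errors.

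Finally, the protocol does not declare the arms comparable after a non-significant test, it analyses intake frequency in any event, and nothing in the documents suggests that excess use would fall in the Lomatuell Pro arm.

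**Conclusion.** The point holds as a flaw in the robustness check. A non-significant gate leaves the primary result unchecked for analgesic cover, and under the stated assumptions the gate misses a 10- to 15-point excess about 26-75% of the time. The logical defect does not depend on the assumed rates; the percentages do.

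The effect on the claim is modest and depends on direction: 0.9 points in one constructed setting (3.6% against 2.7%), 0.4 points with UrgoTul near its planned 95% (4.1% against 3.7%), and a conservative procedure (2.1%) if the excess is in the UrgoTul arm. These figures assume that the triggered adjustment yields a proper interval against -10%, which 7.9.1.2 does not specify because a Mantel-Haenszel test alone gives none. They also ignore the requirement that PP and mITT both succeed. The documents do not support the stronger reading that an unadjusted non-inferiority claim is invalid whenever the gate fails to trigger.

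**What to change.** In Protocol 7.9.1.2, delete the condition that a significant intake difference triggers adjustment, and carry the change into the SAP for this trial. Keep the unadjusted risk difference as the fixed primary analysis in PP and mITT. Then, whatever any p-value shows:

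1. Report the between-arm difference in the proportion with an analgesic taken within 2 hours before the V2 removal, with its 95% CI.
2. Report, in PP and mITT, the risk difference in VAS < 30 mm stratified by that variable, with its lower one-sided 97.5% limit against -10%, as a supportive analysis.
3. If the stratified limit falls below -10% while the unadjusted one does not, state that the conclusion is not robust to analgesic cover.

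The cost is one paragraph and two table rows; the hour of intake is already recorded. The downside is that V2 intake is post-randomisation, so the stratified result is supportive only, and the conclusion may read slightly less favourably.
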